10.5.1 Suggested dose modifications

Starting dose	Dose level -1	Dose level -2		
40 mg/m ² (weekly)	30 mg/m² (weekly)	20 mg/m ² (weekly)		

Starting dose	Dose level -1	Dose level -2
30 mg/m ² (weekly)	20 mg/m ² (weekly)	Discontinue cisplatin

Starting dose	Dose level -1	Dose level -2
100 mg/m ² (q21 days)	75 mg/m ² (q21 days)	50 mg/m ² (q21 days)

10.5.2 Hematologic Toxicity

NCI CTCAE Toxicity Grade (v 4.03)	Cisplatin dose at start of subsequent week
Neutropenia	
1 (1500-1999/mm³)	Maintain dose level
2 (1000-1499/mm³)	Maintain dose level
3 (500-999/mm³)	Hold dose for one week; if continues >7 days
	then decrease 1 dose level and resume when
	reaches grade 2.
4 (<500/mm³)	Hold dose for one week; if continues >7 days
	then decrease 1 dose level and resume when
	reaches grade 2.
Neutropenic Fever (grade3 or 4)	Hold dose at least one week; if ANC ≥1500
	then decrease 1 dose level.
Thrombocytopenia	
1 (75,000/mm ³ -LLN)	Maintain dose level
2 (50,000-74,999/mm³)	Hold dose for one week; if continues >7 days
	then decrease 1 dose level and resume when
	reaches grade 1
3 (25,000-49,999/mm³)	Hold dose for one week; if continues >7 days
	then decrease 1 dose level and resume when
	reaches grade 1
4 (<25,000/mm³)	Hold dose for one week; if continues >7 days
	then decrease 1 dose level and resume when
	reaches grade 1

10.5.3 Non-hematologic Toxicity

NCI CTCAE Toxicity Grade (v 4.03)	Cisplatin dose at start of subsequent week
Renal-serum creatinine	
Cr ULN-1.5mg/dL or CrCl >50 mL/min	Maintain dose level
>1.5mg/dL and CrCl 40-50 mL/min	Decrease by 1 dose level
Cr >1.5mg/dL and CrCl <40	Hold drug until CrCl is >50mL/min the
	resume after decrease by 1 dose level
Fatigue	Decrease by 1 dose level
Grade 3	
Nausea/vomiting	
≤ Grade 2 with maximal medical	Maintain dose level
management	
Intolerable grade 2 with maximal	Decrease by 1 dose level
medical management	
≥ Grade 3 with maximal medical	Hold drug until ≤ grade 2 then resume
management	at one lower dose level
Mucositis in RT field	Hold drug until ≤ grade 3

Grade 4			
Hearing impairment or tinnitus			
≤ Grade 1	Maintain current dose		
Grade 2	Decrease dose by one dose level		
Grade 3	Hold drug until ≤ grade 1 then resume		
	at one lower dose level		
Grade 4 (hearing impairment)	Discontinue cisplatin		
Other grade 4 non-hematologic AEs	Hold drug until ≤ grade 1 then resume		
	at one lower dose level		

10.6 Adverse Events

- Nephrotoxicity (kidney damage) is a major concern. The dose is reduced when there
 is a significant change in the patient's creatinine clearance (a measure of renal
 function). Adequate hydration and diuresis is used to prevent renal damage. The
 nephrotoxicity of platinum-class drugs seems to be related to reactive oxygen
 species and in animal models can be ameliorated by free radical scavenging agents
 (e.g., amifostine). Nephrotoxicity is a dose-limiting side effect [53].
- Neurotoxicity (nerve damage) can be anticipated by performing nerve conduction studies before and after treatment. Common neurological side effects of cisplatin include visual perception and hearing disorder, which can occur soon after treatment begins [54]. While triggering apoptosis through interfering with DNA replication remains the primary mechanism of cisplatin, this has not been found to contribute to neurological side effects. Recent studies have shown that cisplatin noncompetitively inhibits an archetypal, membrane-bound mechanosensitive sodium-hydrogen ion transporter known as NHE-1 [55]. It is primarily found on cells of the peripheral nervous system, which are aggregated in large numbers near the ocular and aural stimuli-receiving centers. This noncompetitive interaction has been linked to hydroelectrolytic imbalances and cytoskeleton alterations, both of which have been confirmed *in vitro* and *in vivo*. However, NHE-1 inhibition has been found to be both dose-dependent (half-inhibition = 30 μg/mL) and reversible [56].
- Nausea and vomiting: Cisplatin is a highly emetogenic chemotherapy, but this symptom is managed with prophylactic antiemetics (ondansetron, granisetron, etc.) in combination with corticosteroids. Aprepitant combined with ondansetron and dexamethasone has been shown to be better for highly emetogenic chemotherapy than just ondansetron and dexamethasone.
- Ototoxicity (hearing loss): There is at present no effective treatment to prevent this side effect, which may be severe although doses >50 mg/m² may be associated with a higher risk of hearing loss. Audiometric analysis may be necessary to assess the severity of ototoxicity. Other drugs (such as the aminoglycoside antibiotic class) may also cause ototoxicity, and the administration of this class of antibiotics in patients receiving cisplatin is generally avoided. The ototoxicity of both the aminoglycosides and cisplatin may be related to their ability to bind to melanin in the stria vascularis of the inner ear or the generation of reactive oxygen species.
- Electrolyte Disturbance: Cisplatin can cause hypomagnesaemia, hypokalaemia, and hypocalcaemia. The hypocalcaemia seems to occur in those with low serum magnesium secondary to cisplatin, so it is not primarily due to the cisplatin.

- Myelotoxicity: This agent can also cause profound bone marrow suppression [57].
- Hemolytic anemia can be developed after several courses of cisplatin. It is suggested that an antibody reacting with a cisplatin-red-cell membrane is responsible for hemolysis [58].
- Other potential adverse events include: ocular disturbances, renal toxicity (with an
 elevation of BUN and creatinine and impairment of endogenous creatinine
 clearance, as well as renal tubular damage, which appears to be transient), and
 hyperuricemia. Much more severe and prolonged toxicity has been observed in
 patients with abnormal or obstructed urinary excretory tracts.

Summary of possible side effects related to cisplatin are:

COMMON, SOME MAY BE SERIOUS

In 100 people receiving cisplatin, more than 20 and up to 100 may have:

- Nausea, vomiting
- Infection, especially when white blood cell count is low
- Anemia, which may cause tiredness or may require blood transfusions
- Bruising, bleeding
- Kidney damage, which may cause swelling, may require dialysis
- Hearing decrease, including ringing in ears
- Change in taste

OCCASIONAL, SOME MAY BE SERIOUS

In 100 people receiving cisplatin, from 4 to 20 may have:

- Allergic reaction, which may cause rash, low blood pressure, wheezing, shortness of breath, swelling of the face or throat
- Confusion
- Difficulty with balance
- Numbness in the fingers and toes
- Low blood pressure
- Low magnesium in the blood, which may cause heart beat irregularities that are possible life threatening

RARE, AND SERIOUS

In 100 people receiving cisplatin, 3 or fewer may have:

- Cancer of bone marrow later in life caused by chemotherapy
- Seizure

10.6.1 Risks of Phlebotomy

Drawing blood or inserting an intravenous catheter into an arm vein may result in bruising or swelling in the area of the insertion, bleeding at the site of the needle puncture, light headedness, fainting, and very rarely, local infection, which may be severe. These risks are reduced by the fact that the blood will be drawn by a qualified physician, nurse or phlebotomist (a professional trained to draw blood).

10.7 Supply

Cisplatin is manufactured by multiple sources and commercial drug will be used in this study.

11 STUDY DRUG (BMX-001)

11.1 Names, Classification, and Mechanism of Action

BMX-001 (Figure 2) also known as MnTnBuOE-2-PyP5+ (manganese butoxyethyl pyridyl porphyrin), is a metalloporphyrin antioxidant that has anti-inflammatory, anti-oxidant, and anti-tumor functions. A series of metalloporphyrins have undergone preclinical evaluation, and BMX-001 represents one with increased catalytic potency along with high lipophilicity. This class of metalloporphyrins leads to inactivation of reactive oxygen species and in turn leads to reduction of oxidative stress. The lipophilicity of BMX-001 leads to its accumulation in the brain parenchyma, and it has been shown to cross the blood-brain barrier. Because the vasculature of most mammalian species is highly sensitive to an oxidative shift, there is a concern for blood pressure monitoring in studies of the metalloporphyrin compounds. Studies in Sprague-Dawley rats showed that intravenous delivery of metalloporphyrin could lead to transient hypotension [59]. In this same study, mice, guinea pigs, dogs, and baboons received intravenous delivery of metalloporphyrins with less effect on blood pressure. BMX-001 was patented by Duke University and has been licensed to BioMimetix JV, LLC.

Figure 2: Chemical Structure of BMX-001

11.2 Potential Benefits

The potential benefits may include protection against mucositis and xerostomia caused by RT of the subject's head and neck cancers [19]. Because this clinical protocol is experimental, it cannot be guaranteed that subjects will receive any benefit as a result of participating in this research study. The information collected in this research may help scientists better understand the mechanisms involved in oxidative stress as it pertains to treatment of head and neck cancer. If such an understanding emerges from this research, it may benefit society by furthering the development of improved treatment methods for newly diagnosed head and neck cancers in the future.

11.3 Packaging and Labeling

11.3.1 Drug Product Formulation and Manufacture

The drug will be supplied by BioMimetix JV, LLC. The drug substance (1.2 kg of solid) was manufactured and stored according to cGMP by Albany Molecular Research, Inc. (AMRI).

BioMimetix JV, LLC, has contracted with AMRI (Glasgow) Ltd. to manufacture single dose vials of sterile BMX-001 for injection. Manufacturing will be conducted on AMRI's Flexicon FPC50W filling machine, which is dedicated for aseptic GMP manufacturing within a clean room suite. Manufacturing will include batch pre-filtration and aseptic filtration and filling in accordance with AMRI Glasgow's validated process.

BMX-001 will be formulated as a solution in 0.9% saline at 10 mg/mL, aseptically filtered and filled to 2 mL in a 5 mL Type 1 clear glass vial, sealed with a 20 mm Flurotec serum stopper and flip off aluminum overseal. A nitrogen overlay will be applied to each vial following filling and prior to stoppering.

In-process testing will include pre-filtration bioburden, post-use filter integrity test, and in-process weight checking. Release tests and specifications for BMX-001 for injection are currently under development, but will be established before manufacturing of the clinical batch commences. These will include sterility (USP <71>), bacterial endotoxins (USP <85>), particulate matter (USP <788>), appearance, color and clarity, pH, osmolality, assay, and purity.

The clinical batch of drug product will be placed on stability and tested for the duration of its use during the clinical trials.

11.3.2 Labels for BMX-001 for Injection, 10 mg/mL

An exemplary label for the BMX-001 for Injection, 10 mg/mL is reproduced in Figure 3.

BMX-001 for Injection, 10 mg/mL

Lot # P07715

Administer SQ, ≤1.4 mL/site.

Caution: New Drug – Limited by Federal

Law to Investigational Use

Emergency contact: [name], cell [contact] Store at RT

Figure 3: Exemplary Label for BMX-001 for Injection, 10 mg/mL

11.3.3 Syringe and Label for Administration of BMX-001 for Injection, 10 mg/mL

A pharmacist at the clinical study center will prepare the loaded syringe(s) and needle(s) that will be used for subcutaneous administration of the appropriate dose of BMX-001 for Injection, 10 mg/mL (from the Dosing Levels Table in Section 11.5 and 11.6) to the clinical subject. The clinical study center pharmacist will adhere to all USP 797 standards for preparation of sterile products. The subcutaneous needle will be capped and the syringe will be stored at room temperature until use, which should occur within 2 hours.

11.3.4 Multi-Dose Kits

The vials, labeled as described in Section 11.3.1, are packaged in paperboard cartons. The carton label includes the information indicated in Figure 4, where "XXX" is replaced by the number of vials contained in the carton.

Lot # P07715 Store at RT

BMX-001 for Injection, 10 mg/mL Multi-Dose Kit

Contents: XXX Single-Dose Units @ 20 mg each

Caution: New Drug - Limited by Federal Law to

Investigational Use.

Emergency contact: [name], cell [contact]

Figure 4: Exemplary Label for Multi-Dose Kits

11.4 Supply, Receipt, and Storage

The multi-dose kits described in Section 11.3.4 will be shipped by overnight delivery to the local clinical center. These kits will be stored at room temperature, in a locked, physically secure environment, separate from other drug products, according to the local clinical center pharmacy's standard procedures for storage of investigational drug products. Drug accountability records will be maintained by the local clinical center for all clinical trial supplies.

The stability of the drug product during the course of the clinical trial will be established by long-term stability studies currently underway at AMRI (Glasgow) Ltd. At the present time, no significant drug degradation has been observed under storage conditions.

11.4.1 Compliance and Accountability

Drug accountability records will be maintained for all clinical trial supplies.

11.4.2 Disposal and Destruction

All empty and partially used clinical trial supplies will be destroyed in accordance with the institution's requirements for an investigational agent. Disposition of all unused boxes of study drug will be carried out according to instructions provided by BioMimetix JV, LLC, at the end of the study after drug accountability is performed. The pharmacy will maintain detailed documentation of the number and identification of BMX-001 vials that are destroyed, and copies of these documents will be provided to BioMimetix JV, LLC.

11.4.3 Dispensing and Preparation

A pharmacist at the local investigative site will prepare the loaded syringe and needle that will be used for subcutaneous administration of the appropriate dose of BMX-001, Injection Solution 10 mg/mL, as indicated on the vial label, to the clinical subject. The BMX-001, Injection Solution 10 mg/mL will be drawn from the vial described in Section 11.3.1. The subcutaneous needle will be capped and the syringe will be stored at room temperature until use, which should occur within 2 hours.

11.5 Phase 1 Administration by Dose Escalation at levels below established MTD

The RP2D of BMX-001 has been established in a concluded Phase 1 trial with high-grade glioma patients. This head and neck cancer Phase 1 trial evaluated the two lower doses of BMX-001 and found no dose-limiting toxicities of BMX-001 in combination with cisplatin and also with radiation of the head and neck.

BMX-001 was administered subcutaneously as a loading dose before starting concurrent chemoradiation (days -4 through 0 depending on patient scheduling). After the loading dose, the maintenance dose levels were given two times per week for 8 weeks. The starting dose level was 7 mg loading dose. The BMX-001 dose was then escalated to 14 mg loading dose. After the loading dose, the BMX-001 maintenance dose was administered 7 mg twice a week.

The corresponding volumes of BMX-001, Injection Solution 10 mg/mL associated with the loading doses are as follows:

0.7 mL/subject loading dose = 7 mg/subject

1.4 mL/subject loading dose = 14 mg/subject

The corresponding maintenance doses would be equivalent to the following:

0.35 mL/subject maintenance dose = 3.5 mg/subject

0.7 mL/subject maintenance dose = 7 mg/subject

BMX-001 is administered by subcutaneous injection of a sterile 10 mg/mL solution in saline. The subcutaneous injections are at any optimum site on the torso, the upper leg or upper arm. Maintenance doses are approximately one-half the size of the loading dose and should be administered twice weekly. The first maintenance dose should be delivered either 3 or 4 days after the loading dose and subsequent maintenance doses delivered at 3 to 4 day intervals to average 2 doses per week.

Table – Dosing Levels for Groups I & II							
	Group I Group II						
Loading Dose	7 mg/Subject	14 mg/Subject					
Maintenance Dose							
1	3.5 mg	7 mg					
2	3.5 mg	7 mg					
3	3.5 mg	7 mg					
4	3.5 mg	7 mg					
5	3.5 mg	7 mg					
6	3.5 mg	7 mg					
7	3.5 mg	7 mg					
8	3.5 mg	7 mg					

11.6 Phase 2 Expanded

Because this Phase 2 trial involves neck radiation instead of brain and cisplatin instead of TMZ, a safety lead in studying the RP2D of 28 mg/subject load and 14 mg/subject maintenance dose will be part of Phase 2 expansion.

No more than 1.4 mL is to be administered at a single injection site. Thus a 28 mg dose will be administered in two equal portions (14 mg), taken from different vials and injected via separate syringes and needles at two different sites.

Dose Level for Phase 2						
Loading Dose	28 mg/Subject					
Maintenance Dose						
1	14 mg					
2	14 mg					
3	14 mg					
4	14 mg					
5	14 mg					
6	14 mg					
7	14 mg					
8	14 mg					

11.7 Compliance and Accountability

Drug accountability records will be maintained for all clinical trial supplies. Study team staff will schedule all of the patient's appointments and a calendar may be provided to the patient.

Regardless of the reason for holding study drug treatment, the maximum allowable length of treatment interruption is 3 weeks.

11.8 Concomitant Medications

Because corticosteroids are anti-inflammatory and could interrupt oxidative stress, patients will be required to be on stable or decreasing corticosteroids dose at the time of the study enrollment. If patient is required to have additional steroids such as an allergic reaction, adrenal insufficiency, increased neurological symptoms, and/or increased intracranial pressure, then corticosteroids can be added at the discretion of the treating physician and minimal dose, if deemed medically appropriate, will be utilized to control symptoms.

11.9 Dose Modifications

If adverse events occur that require holding BMX-001, the dose will remain the same once treatment resumes.

NCI CTCAE toxicity	BMX-001 dose
Hypotension	
≤ Grade 2	Maintain current dose. For grade 2
	may give IV fluids and place patient
	in Trandeleburg position.
≥ Grade 3	Discontinue BMX-001. Supportive
	care as below.
Injection site reaction	
≤ Grade 2	Administer acetaminophen 325-650
	mg PO 30 minutes prior to injection.
Intolerable grade 2	Hold drug until ≤ grade 1 then
_	resume. Supportive care as below.
≥ Grade 3	Discontinue BMX-001.

NCI CTCAE toxicity	BMX-001 dose
Other \geq grade 3 attributable to	Discontinue BMX-001.
BMX-001	
Electrocardiogram QT corrected	
interval prolonged	
Grade 1 (Average QTc 450 - 480 ms)	Maintain current dose.
Grade 2 (Average QTc 481 - 500 ms)	Hold BMX-001 pending review by
	sponsor. Refer to cardiology.
	ECG should be re-checked in
	approximately 1 week after the QTc
	prolongation was first observed or
	more frequently as clinically
	indicated.
Grade 3 (Average QTc >= 501 ms;	Discontinue BMX-001.
>60 ms change from baseline)	

Regardless of the reason for holding study drug treatment, the maximum allowable length of treatment interruption is 3 weeks.

11.10 Management Guidelines for Potential BMX-001-induced Toxicities

Any toxicity associated or possibly associated with BMX-001 treatment should be managed according to standard medical practice unless as specified above. The primary anticipated toxicity is hypotension, which should resolve within 30-60 minutes.

11.10.1 Post Drug Administration Monitoring

Subjects should be observed for a minimum of 2 hours after administration of the initial loading dose of BMX-001 and for a minimum of 1 hour after subsequent doses. Monitoring should include evaluation of blood pressure, heart rate, and skin reaction. Blood pressure and heart rate will be measured pre-dose and then after 30 (\pm 5), 60 (\pm 5), and 120 (\pm 10) minutes on the loading dose. It will be checked pre-dose, 30 (\pm 5), and 60 (\pm 5) minutes all other days of BMX-001 administration. The skin reaction at the injection site should be evaluated at the same time blood pressure and heart rate are monitored. Site(s) of prior drug injection will be inspected before each new drug administration.

After discharge, patient should be advised to be alert for potential symptoms of low blood pressure (i.e., dizziness, fainting, lightheadedness, blurry vision, weakness, nausea, vomiting, including exaggeration of one of the previous symptoms when transitioning from lying or sitting to standing). If these symptoms occur after discharge, the patient should lie down, elevate his/her feet and contact their health care provider if the symptoms persist.

11.10.2 Hypotension

If after drug therapy, the blood pressure drops > 20 mm Hg (systolic) from the pre-injection blood pressure level, place the patient in supine position and treat as follows:

Mild hypotension (systolic > 90 mm Hg and < 110 mm Hg, or postural hypotension only) observe patient with repeated measures of blood pressure and heart rate every 10 minutes and expect

resolution within 30-60 minutes. Observe patient in the outpatient setting until blood pressure returns to normal and patient has no hypotensive or postural hypotensive symptoms.

Moderate hypotension (systolic > 70 mm Hg and < 90 mm Hg) treat with i.v. fluids (normal saline or Ringer's lactate) with repeated measures of blood pressure and heart rate every 10 minutes until systolic BP > 110 mm Hg. Observe patient in the outpatient setting until blood pressure returns to normal and patient has had no hypotensive or postural hypotensive symptoms for at least 1 hour.

Severe hypotension (systolic < 70 mm Hg) treat with bolus i.v. fluids (normal saline or Ringer's lactate) with repeated measures of blood pressure and heart rate every 5 minutes until systolic BP > 110 mm Hg. If resolution is not prompt, consider evaluation for underlying cardiovascular disease (including ECG) and urgent consultation with critical care team. Observe patient until blood pressure returns to normal and patient has had no hypotensive or postural hypotensive symptoms for at least 1 hour.

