6.2 Conditions for Patient Ineligibility (Exclusion Criteria)

- 1) Stage I or II; T1N1 and T2N1 stage III presentations per AJCC 7th edition
- 2) Distant metastasis
- 3) Hypertension requiring 3 or more anti-hypertensive medications to control
- 4) Grade ≥2 hypotension at screening
- 5) Requirement for concurrent treatment with nitrates or other drugs that may, in the judgment of the treating investigator, create a risk for a precipitous decrease in blood pressure
- 6) History of syncope within the last 6 months
- 7) Patients receiving, or unable to stop use at least 1 week prior to receiving the first dose of BMX-001, medications listed in Section 12.2 of the protocol are not eligible.
- 8) Pregnancy or women of childbearing potential and men who are sexually active and not willing/able to use medically acceptable forms of contraception; this exclusion is necessary because the treatment involved in this study may be significantly teratogenic
- 9) Women who are breast feeding are not eligible
- 10) Prior allergic reaction to cisplatin
- 11) Known hypersensitivity to compounds of similar chemical composition to BMX-001
- 12) Grade 3-4 electrolyte abnormalities (CTCAE v 4.03) except sodium, which must be ≥126 mmol/L.
- 13) Prior unrelated malignancy requiring current active treatment with the exception of cervical carcinoma *in situ*, basal cell carcinoma of the skin, resected T1-2N0M0 differentiated thyroid cancers, invasive cancers with a 3-year disease-free interval, Ta bladder cancers, or low and favorable intermediate risk prostate cancer.
- 14) Prior history of HNSCC receiving radiation or chemo-radiation.

- 15) Prior systemic chemotherapy for the study cancer (including neoadjuvant chemotherapy); note that prior chemotherapy for a different cancer is allowable.
- 16) Prior radiotherapy that would result in overlap of radiation treatment fields with planned treatment for study cancer.
- 17) A marked baseline prolongation of QT/QTc interval (e.g., repeated demonstration of a QTc interval >480 milliseconds (ms) (CTCAE grade 1) using the specific/usual choice by clinical center for correction factor.
- 18) A history of additional risk factors for Torsades de Pointes (e.g., congestive heart failure, hypokalemia, known family history of Long QT Syndrome).
- 19) Severe, active co-morbidity, defined as follows:

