7.2 Screening Examination

The screening examination will take place within 21 days prior to starting BMX-001. The screening evaluation and baseline evaluation may be combined. Standard of Care assessments (such as performance status, labs and imaging) completed per inclusion and exclusion criteria but prior to signing ICF may be utilized for eligibility purposes. An informed consent must be signed by the patient before any screening procedures take place. Subject data to be collected at the Screening Examination includes physical examination, vital signs, height (may be done at baseline), weight, laboratory studies (complete blood count with differential, complete metabolic panel and PT/aPTT), past medical history, and concomitant medications. Mucositis assessment will be done at the screening visit. Assessment of measurable disease by imaging will be done per standard of practice at each institution.

Physical, vital signs (temperature, respiratory rate, blood pressure, and pulse), height (done once at screening or baseline), weight, ECG, and mucositis must be performed at baseline (Day -4 to 0). Saliva production and questionnaires will also be done at baseline. Serum beta-HCG is measured on women of childbearing potential no more than 48 hours prior to the first dose of BMX-001.

8 Registration Procedures and Administrative Considerations

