11.11.1 Non-hematologic

The occurrence of non-hematologic grade 3 or greater adverse events considered to be possibly, probably, or definitely related to BMX-001 during treatment with BMX-001, excluding grade 3 alopecia and elevation in alkaline phosphatase, grade 3 nausea or vomiting unless occurring despite the use of standard anti-emetics.

> 14 day delay to re-treat due to failure to resolve any grade 3 or greater non-hematologic drugrelated toxicity to re-treatment criteria or pre-treatment baseline.

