13.2 Re-treatment Criteria

Patients must not be experiencing a DLT in order to be retreated. Other dose modifications are specified in sections 10.5.1 (cisplatin) and 11.9 (BMX-001).

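### Section 11.9 has no hold step for grade 2 hypotension already present before a BMX-001 injection, although that grade excludes a patient at screening and pressure is read before every dose

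*Combined protocol and SAP*

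**What the plan says.** Entry: exclusion criterion 4 in Section 6.2 is "Grade ≥2 hypotension at screening". Under Section 7.2, "The screening examination will take place within 21 days prior to starting BMX-001". Vital signs are taken again at baseline (Day -4 to 0), but no action threshold is given for them.

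Monitoring: for the loading dose, Section 11.10.1 states "Blood pressure and heart rate will be measured pre-dose and then after 30", 60 and 120 minutes. On all other dosing days the readings are pre-dose and at 30 and 60 minutes. Section 13.1.3 also requires a pre-dose reading on every dosing day. Neither section says what a low pre-dose reading should lead to.

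Dosing: in Section 11.9 the hypotension row for grade 2 or lower begins "Maintain current dose. For grade 2" and goes on to permit IV fluids and positioning. The row for grade 3 or higher discontinues BMX-001. In the same table, grade 2 QTc prolongation reads "Hold BMX-001 pending review by" the sponsor, and an intolerable grade 2 injection-site reaction is also held.

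Re-treatment: Section 13.2 says "Patients must not be experiencing a DLT in order to be retreated" and otherwise refers back to 11.9.

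Acute care: the steps in Section 11.10.2 begin "If after drug therapy, the blood pressure drops > 20 mm Hg (systolic) from the pre-injection blood pressure level". Only then do its absolute classes apply: mild above 90 and below 110, moderate above 70 and below 90, severe below 70 mm Hg systolic.

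**The concern.** A state that keeps a patient out of the trial at screening does not, under any written rule, delay an injection once the patient is in it. The one dose instruction that mentions grade 2 hypotension says to continue. It is limited by neither timing nor cause.

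This matters because hypotension is the toxicity that Section 11.10 chiefly expects of BMX-001, and Section 11.12 gives a vasodilating mechanism for it. Low pre-dose readings are also foreseeable: Section 10.6 lists low blood pressure among cisplatin effects seen in 4 to 20 of 100 people. The sponsor already treats added vasodilation as a hazard, since nitrates and similar drugs are excluded in 6.2 and prohibited in 12.2.

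At stake is an avoidable hypotensive event. If it reaches grade 3, 11.9 also ends BMX-001 for that patient.

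**Working it through.** The plan gives no figure on this point to reproduce. The check sets the rules side by side and then applies the 11.10.2 trigger to low starting pressures.

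**Step 1: where a pre-dose rule could sit.**

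| Place | What it does | Rule for grade 2 hypotension before an injection? |
|---|---|---|
| 6.2, criterion 4 | excludes grade 2 or higher | at screening only |
| 7.2 | screening within 21 days; vital signs again at Day -4 to 0 | no threshold |
| 11.10.1, 13.1.3 | pressure read before every injection | no action stated |
| 11.9, grade 2 or lower | dose maintained; fluids and positioning at grade 2 | no hold |
| 11.9, grade 3 or higher | BMX-001 discontinued | does not reach grade 2 |
| 13.2 | bars re-treatment during a DLT, else refers to 11.9 | no; a non-hematologic DLT is grade 3 or greater (11.11.1) |
| 11.10.2 | care after a post-injection fall | no |

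If the 11.9 row covers any grade 2 hypotension, it says to continue. If it covers only falls caused by an injection, no rule addresses the pre-dose state. The gap remains on either reading.

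**Step 2: how often a reading is taken with no action attached.** Section 13 schedules one loading dose and twice-weekly maintenance in weeks 1 to 8: 1 + 2 × 8 = 17 injections per patient, each with a pre-dose reading.

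**Step 3: the relative trigger at low starting pressure.** Let b be the pre-injection systolic and s the later reading, in whole mm Hg. Care opens when b − s > 20, so first at s = b − 21. A fall of exactly 20 does not open it.

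| b | Class of b | Largest fall that does not trigger ends at b − 20 | Trigger first opens at b − 21 |
|---|---|---|---|
| 71 | moderate | 51 (severe) | 50 (severe) |
| 75 | moderate | 55 (severe) | 54 (severe) |
| 80 | moderate | 60 (severe) | 59 (severe) |
| 85 | moderate | 65 (severe) | 64 (severe) |
| 89 | moderate | 69 (severe) | 68 (severe) |
| 92 | mild | 72 (moderate) | 71 (moderate) |

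For every b from 71 to 89 the trigger opens at 50 to 68, inside the severe class. The lowest starting pressure from which it can open in the moderate class is 92. A patient who goes from 85 to 65 is below the severe cut-off, yet the 11.10.2 steps have not been triggered.

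**Step 4: what still applies before the trigger opens.** The 11.9 grade 2 measures and the appeal in 11.10 to standard medical practice do not depend on the 20 mm Hg fall. Such a patient is not without care, but the pressure-specific steps are not yet in force.

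**The case against.** The strongest reply is that the 11.9 row concerns falls after an injection. Its measures are acute care, and 11.10 expects hypotension to resolve within 30 to 60 minutes, so keeping the dose after a transient fall makes sense. That is a fair reading of intent, but it leaves the pre-dose state with no rule.

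The second reply is that there are safeguards: baseline vital signs, the exclusion of recent syncope and of pressure-lowering drugs, hydration with cisplatin, one to two hours of observation, and clinical discretion. All of these stand. They lower the risk and keep the point minor, but none tells the site what to do with a low reading.

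The QTc comparison is limited, since that toxicity has its own cardiology work-up. It shows only that the table already uses hold steps.

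A reader might infer more than the documents support:

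- *That nothing limits dosing short of a DLT.* The 11.9 row for grade 3 or higher discontinues BMX-001 with no attribution condition, so a limit exists there whether or not the event is a DLT.
- *That such events would distort the DLT count or the lead-in decision.* Section 11.11.1 does count "The occurrence of non-hematologic grade 3 or greater adverse events considered to be possibly, probably, or definitely related to BMX-001", but 11.11 also requires the event to be assessed as unrelated to concomitant medication or intercurrent illness. Under 4.3.2 the lead-in criteria concern definite BMX-001-related events, and the accrual pause needs grade 4 or 5. A grade 3 event of mixed cause, judged possibly related, meets neither.
- *That the cisplatin range gives the number of affected injections.* The listing carries no grade and no pressure value, and nothing says how often low pressure falls on a dosing day.

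**Conclusion.** The point holds as a minor, cheap patient-safety improvement. Section 11.9 goes from maintaining BMX-001 at grade 2 hypotension to discontinuing it at grade 3, with no hold between, and no other text says to withhold an injection when grade 2 hypotension is already present. For a pre-injection systolic of 71 to 89 mm Hg, the 11.10.2 trigger adds its steps only at 50 to 68.

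The textual gap rests on no numerical assumption. The pressure range assumes whole-number readings. It uses the mm Hg classes of 11.10.2, whereas the dosing rules use CTCAE grade; the documents do not map one to the other, so 71 to 89 illustrates the trigger and does not define grade 2. The frequency of affected injections cannot be estimated from the documents.

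**What to change.** At the next amendment:

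1. In the 11.9 hypotension row, keep the grade 2 fluids and positioning text and add: *If grade 2 hypotension is present before an injection, whatever the cause, do not inject; treat and recheck, inject at the same dose once grade 1 or below, otherwise omit that dose (3-week limit applies).*
2. Leave the discontinuation rule for grade 3 or higher unchanged, and add no attribution condition to it.
3. In 11.10.1 add: *The pre-dose blood pressure must be reviewed before injecting (see 11.9).*
4. Keep the 20 mm Hg trigger in 11.10.2.

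The rule fits what is already there: 11.9 resumes at the same dose after a hold and limits interruptions to three weeks. Pre-dose pressure is already measured, so no new procedure or data item is needed. The cost is a small number of delayed or omitted injections.

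Editorial only: readings of exactly 70 or 90 mm Hg fall in no class in 11.10.2. Setting mild at 90 to below 110 and moderate at 70 to below 90 closes this.
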